Building on this work and in response to calls in the literature to explicitly examine changes in perceived drinking norms and alcohol outcomes in PNF intervention studies (e.g., Dempsey et al., 2018), this study employed a large and diverse sample of incoming college students attending universities in Texas and California to (1) examine the effectiveness of a fully featured CampusGandr smartphone app as an alcohol intervention strategy when advertised to students as a social game about college life free to play over their fall semester; and, (2) elucidate the optimal dosage of alcohol feedback to be delivered in the app to best reduce perceptions of drinking norms and alcohol consumption. First, using an intent-to-treat approach, we examine short and longer-term effects on alcohol use and perceptions of drinking norms associated with a CampusGandr intervention period in which student users were randomized to receive alcohol feedback in 0, 3, or 6 weeks of the game. Second, we take a closer look at the question of dosage by examining end-of-semester drinking and perceptions of norms as a function of the number of alcohol feedback results verifiably viewed by participants. Whereas a traditional alcohol intervention approach might assume that delivering alcohol feedback every week would be most protective, our pilot work (Boyle et al., 2018) and a large psychological reactance literature (e.g., Dillard et al., 2023; Jung et al., 2010; Reynolds-Tylus et al., 2022, 2024) suggest that too much feedback on alcohol relative to other topics in the game may reveal the drinking-reduction intention of the activity, eliciting reactance, and thereby undermining efficacy. As such, less frequent alcohol feedback balanced with feedback on other topics of interest to students was expected to be more efficacious in reducing perceived drinking norms, preventing alcohol

initiation, and reducing consumption than both no alcohol feedback and more frequent alcohol feedback.

Design

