This study utilized a three-arm parallel-group randomized controlled trial to examine the efficacy of CampusGandr as a gamification approach to multi-dose PNF for reducing first-year college students' alcohol use. Outcomes were conceptualized in three domains: (1) descriptive norms, (2) alcohol consumption (drinks during a typical week and during one's heaviest drinking occasion), and (3) alcohol-related consequences. All assessments and interventions were implemented remotely, and participants did not interact directly with any research staff. To examine long-term effects, outcomes were measured at 4, 9, and 12 months after baseline.

Participant Recruitment

The present study's primary recruitment sites were a large, public university in Texas (TX) and a small, private college in California (CA). At the beginning of the 2022 and 2023 fall semesters, incoming students from these two universities were invited to create a CampusGandr account via emails and in-person information booths on campus. From Weeks 5 to Week 8, app users were invited to join the study as "Official Testers" and receive \$25 in gift cards for completing the baseline survey. Concurrently, students who didn't yet have accounts were invited via school email to become Official Testers by completing the baseline survey, downloading and creating a CampusGandr account, and begin playing the rounds. All recruitment materials and procedures were reviewed and approved by the universities' IRBs.

To improve participant enrollment for Fall 2023, recruitment efforts were supplemented through BuildClinical (BC), a digital platform specializing in targeted research recruitment. BuildClinical designs and deploys advertisements across a range of online channels, including search engines (e.g., Google) and social media platforms (e.g., Instagram, Snapchat, and Facebook). For this study, BC developed tailored advertisements targeting incoming first-year students at four-year public and private universities in Texas and California (to align with the study's in-person recruitment sites). Individuals who clicked on the ads were directed to a landing page and then a screening survey hosted by BC to assess eligibility. Eligible leads were then directed to our survey hosted on Qualtrics, where we obtained informed consent and administered the survey and invited them to download and play the game.

Procedure

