In total 2,898 students consented and then took the baseline survey and/or played CampusGandr. Of those, 1,143 students were considered fully enrolled in the study, as they provided consent, completed the baseline survey, and played at least one round of CampusGandr. Participants were randomized using an automated urn strategy so that each of the three conditions were filled evenly by a gender and baseline drinking status (any, none). All PNFs were delivered remotely and automatically; therefore, participants, but not researchers, were blind to allocation. Based on condition assignment, participants could see up to 6 alcohol feedbacks (More Alcohol Feedback; MAF), up to 3 alcohol feedbacks (Less Alcohol Feedbacks; LAF) or 0 alcohol feedbacks (No Alcohol Feedback; NAF) during the weekly game. Participants were unaware of study condition, and randomization was not based on any variables. Condition assignment to the LAF and MAF conditions did not guarantee that the participants played the round (i.e., estimating their peers' answer and providing their own answer) and viewed the results (i.e., PNF). Approximately 31% ($n=130$) of participants in the MAF condition saw all 6 alcohol feedbacks and 37% ($n=137$) of participants in the LAF condition saw all 3 alcohol feedbacks. On average, participants in the MAF condition saw 3.0 alcohol feedbacks ($SD=2.6$), and participants in the LAF condition saw 1.5 alcohol feedbacks ($SD=1.3$).

Survey Measures

Descriptive Drinking Norms

Estimates of peers' drinking quantity was measured using the Drinking Norms Rating Form (Baer, 1994). Participants reported the number of standard drinks they believed that a same-gender peer consumed on each day of the week (e.g., a typical Friday, a typical Saturday) in the past 30 days. Participants were asked to think about, "a typical [*male/female/student*] at [*specific college name*]" when answering. Responses were summed across the 7 days, and the sums were truncated at 80.

Injunctive Drinking Norms

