The Injunctive Norms Questionnaire (Baer, 1994) assessed participants' personal approval and perceptions of the approval of a typical same-sex first-year student at their specific university for five risky drinking behaviors including "playing drinking games," "drinking shots," "drinking to get drunk," "drinking alcohol every weekend," and "drinking under age 21." Response options ranged from 1 (*strongly disapprove*) to 7 (*strongly approve*). Internal consistency was high in $\alpha = .89$ for and responses were averaged to create a composite score.

Heaviest Drinking Occasion (Peak Drinks)

Participants were instructed to think about their drinking in the past 30 days and respond to the question, "What is the maximum number of drinks you drank during any one drinking occasion?" Values were truncated at 30.

Typical Weekly Drinking

Typical drinking was measured using the Daily Drinking Questionnaire (Collins et al., 1985). Participants were asked to report the number of standard drinks they consumed on each day (e.g., a typical Monday, Tuesday) of the week during the past 30 days. Responses were summed across the 7 days, and the sums were truncated at 80.

Alcohol-Related Problems

Problems arising from alcohol use were measured using the Brief Young Adult Alcohol Consequences Questionnaire (Kahler et al., 2005). Participants indicated (no=0, yes=1). if they

had experienced 24 negative experiences after drinking alcohol (e.g., “I have felt very sick to my stomach or thrown up after drinking”). Responses were summed, with total scores ranging from 0 to 24. Cronbach’s alphas were acceptable across the four timepoints ($\alpha=0.89-0.92$).

App Measures

Number of Game Feedbacks Viewed

Whether or not participants viewed each round of game feedback was recorded in the app’s backend. This allowed us to create variables indicative of (1) the total number of feedback viewed; and (2) the number of alcohol-specific feedback viewed.

Statistical Analysis Plan

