A preliminary examination of the outcome distributions revealed that a large proportion of the sample did not drink, and the distributions of outcomes were all positively skewed. A generalized linear mixed modeling approach was used for all analyses. Given the large proportion of non-drinkers, we conducted hurdle-negative binomial mixed models to evaluate peak drinks and alcohol-related problems. Hurdle models are two-part models that independently predict zero versus non-zero counts in one part and values of non-zero counts in the other (Cameron & Trivedi, 2013; Hilbe, 2011). For peak drinks, the zero versus non-zero part of the model predicts whether individuals drank any alcohol using a logistic mixed model. The non-zero counts part of the model uses a truncated (i.e., zeros are removed, and values are subtracted by one) negative binomial mixed model to predict the number of alcoholic beverages consumed during drinkers’ heaviest occasion. Similarly, for alcohol-related problems, whether individuals experienced any alcohol-related problems or not was evaluated with a logistic mixed model, and the number of problems among those who experienced any was examined with a truncated negative binomial mixed model. Analyses examining the typical number of drinks consumed per week focused exclusively on counts, using a truncated negative binomial model; this approach avoided duplicating the logistic part of the peak drinks analysis, which would have occurred if zero versus non-zero values were compared, as this would have resulted in less precision.

Modeling Treatment. The intervention was evaluated using two strategies. The first evaluated conditions using an intent-to-treat (ITT) approach, in which outcomes were analyzed based on condition assignment, regardless of treatment participation and adherence (McCoy, 2017). Extending the short-term analyses presented in LaBrie et al. (2025), the second strategy evaluated outcomes at follow-up as a function of the number of alcohol feedbacks viewed (i.e., 0-6), which helped to eliminate the noise associated with variability in number of alcohol feedbacks viewed within LAF and MAF conditions.

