Modeling Time. To test the intervention’s effects on outcomes at each follow-up, Step 1 of each model evaluated outcomes while controlling for baseline values, sex, site, and follow-up time point. Data from all enrolled participants were utilized in the analyses as modern approaches to handling missing data mostly recover power that would otherwise be lost to attrition (Enders, 2010).

Power. Assuming that the average abstinence rate would be 30% in each condition and baseline outcomes account for 25% of the variance in any drinking at follow-up, the *a priori* power analysis indicated that a sample of 1,200 would yield .89 power to detect abstinence rates as small as 5% lower than control in addition .87 to detect predicted differences among

conditions with rate ratios of 1.2 (i.e., 20% differences or higher between contrast groups). No interim analyses were conducted, nor stopping guidelines were in place.

References

- Arria, A. M., Caldeira, K. M., Allen, H. K., Vincent, K. B., Bugbee, B. A., & O'Grady, K. E. (2016). Drinking like an adult? Trajectories of alcohol use patterns before and after college graduation. *Alcoholism: Clinical and Experimental Research*, 40(3), 583-590.
- Baer, J. S., Stacy, A., & Larimer, M. (1991). Biases in the perception of drinking norms among college students. *Journal of Studies on Alcohol*, 52(6), 580–586.
<https://doi.org/10.15288/jsa.1991.52.580>
- Berkowitz, A.D. (2004). An overview of the social norms approach. In L. Lederman and L. Stewart (Eds.), *Changing the culture of college drinking* (pp. 193–214). Cresskill, NJ: Hampton Press.
- Bensley, L. S., & Wu, R. (1991). The role of psychological reactance in drinking following alcohol prevention messages 1. *Journal of Applied Social Psychology*, 21(13), 1111-1124.
- Bernstein, M. H., Stein, L. A., Neighbors, C., Suffoletto, B., Carey, K. B., Ferszt, G., ... & Wood, M. D. (2018). A text message intervention to reduce 21st birthday alcohol consumption: Evaluation of a two-group randomized controlled trial. *Psychology of Addictive Behaviors*, 32(2), 149-161.
- Borsari, B., & Carey, K. B. (2003). Descriptive and injunctive norms in college drinking: A meta-analytic integration. *Journal of Studies on Alcohol*, 64(3), 331-341.

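### Preventing initiation is a stated hypothesis, but no described analysis separates starting to drink among baseline non-drinkers from a dry month among baseline drinkers

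*Combined protocol and SAP*

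**What the plan says.** - **Hypothesis** (Goals of This Clinical Trial). Less frequent alcohol feedback was "expected to be more efficacious in reducing perceived drinking norms, preventing alcohol" (the sentence continues after a page break) "initiation, and reducing consumption than both no alcohol feedback and more frequent alcohol feedback". Initiation is thus named apart from consumption.
- **Outcomes** (Design). The three domains are descriptive norms, consumption (typical week and heaviest occasion) and consequences. Initiation is not listed or defined.
- **Drinking versus not drinking** (Statistical Analysis Plan). In the peak-drinks hurdle model, "the zero versus non-zero part of the model predicts whether individuals drank any alcohol using a logistic mixed model". The weekly-drinks model adds nothing here: "Analyses examining the typical number of drinks consumed per week focused exclusively on counts, using a truncated negative binomial model".
- **Window** (Heaviest Drinking Occasion). "Participants were instructed to think about their drinking in the past 30 days and respond to the question" about their maximum, so the binary outcome is past-30-day drinking.
- **Population and covariates** (Modeling Time). "Data from all enrolled participants were utilized in the analyses". Step 1 adjusts for baseline values, sex, site and follow-up time point. No later step is described.
- **Allocation** (Procedure). An urn scheme balances on gender and on any versus no baseline drinking. The same paragraph then says that no variables were used for randomization.

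**The concern.** Only a student who is not drinking at baseline can start. In a student who already drinks, the same binary outcome records whether the last 30 days were dry. A baseline main effect gives the two groups different intercepts but leaves one condition odds ratio for both.

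A preventive effect among non-drinkers could therefore be weakened or cancelled in the pooled estimate. Equally, a pooled effect could arise entirely among drinkers. The second case matters for interpretation, because the pooled odds ratio is the only described result that a reader could connect to the initiation hypothesis.

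**Working it through.** **The plan's own figure.** The Power paragraph gives .89 for a 5-point difference in abstinence, with 30% abstinence, 25% of variance explained by baseline and 1,200 students. This is whole-sample abstinence, not initiation. A two-sided 5% two-proportion test of 30% v 25% gives power 0.35 for 400 v 400, 0.45 with variance multiplied by (1 − 0.25), and 0.57 for 400 v 800 with that reduction. A value near .89 needs inputs the plan does not state, such as 1,200 observations per arm (0.887). Alpha, sidedness, contrast, dropout and within-person correlation are not given, so the figure is not reproducible from its stated inputs rather than shown to be wrong. Nothing below depends on it.

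**Inputs.** Enrolled: 1,143 in three arms, so 1,143/3 = 381 per arm. The baseline non-drinker share, onset rate and stopping rate are not in the documents. All three are assumptions here. Calculations use one follow-up and no random effect.

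**1. Effect only in non-drinkers.** Assume a 30% share, control onset 25%, onset odds ratio 0.50, and 90% of drinkers still drinking in both arms.
- Odds 0.25/0.75 = 0.333; halved, 0.167; onset 0.167/1.167 = 14.3%. The fall is 10.7 points among non-drinkers and 0.30 × 10.7 = 3.2 points overall.
- Per arm: 0.30 × 381 = 114 non-drinkers and 267 drinkers.
- Approximate information is n × p(1 − p) at the mean p. Non-drinkers: 114 × 0.196 × 0.804 = 18.0. Drinkers: 267 × 0.90 × 0.10 = 24.0.
- Common log odds ratio ≈ 18.0 × ln(0.50)/(18.0 + 24.0) = −0.297, an odds ratio of 0.74. Fitting the logistic model with arm and baseline status to the expected counts gives **0.75**.
- Range with the onset odds ratio held at 0.50: share 20–50%, control onset 25–40%, drinkers still drinking 80–95%. The fitted common odds ratio runs from **0.57** (50%, 40%, 95%) to **0.87** (20%, 25%, 80%).

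**2. Effect only in drinkers.** Assume a 30% share, onset 30% in both arms, and stopping rising from 10% to 20%. The drinkers' odds ratio is (0.80/0.20)/(0.90/0.10) = 0.44. The baseline-adjusted common odds ratio is **0.63**. In simulation at 400 per arm it was significant in 70% of runs, against 5% for a test confined to non-drinkers.

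**3. Opposite effects.** Assume onset falls from 30% to 20% and stopping falls from 10% to 5%. The common odds ratio is about **1.05**. In simulation it was significant in 6% of runs, against 43% among non-drinkers alone.

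**4. Same total, different cause.** With a 30% share, control abstinence is 0.30 × 0.70 + 0.70 × 0.10 = 28%. Onset falling to 20% gives 0.30 × 0.80 + 0.70 × 0.10 = 31%. Stopping rising to 14.3% instead gives 0.30 × 0.70 + 0.70 × 0.143 = 31%.

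**5. Power among non-drinkers.** At N = 1,200 and a 30% share there are 400 × 0.30 = 120 per arm. For 30% v 20%, the null standard error is √(0.25 × 0.75 × 2/120) = 0.0559 and the alternative one is √((0.30 × 0.70 + 0.20 × 0.80)/120) = 0.0555. Power = Φ((0.10 − 1.96 × 0.0559)/0.0555) = Φ(−0.17) = **0.43**. Over shares and control onset rates of 20–50%, arm-versus-arm power is 0.09–0.26 for 5 points and 0.24–0.80 for 10 points.

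**The case against.** The plan never calls the logistic part a test of initiation. Any drinking in the whole sample is a legitimate outcome, and it is the one the power statement addresses. A reader might infer that the trial will report an effect in drinkers as prevented initiation; that is a prediction about reporting which the text does not support. What stands is that, if this model is not the test, the hypothesis has none.

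The absence of an interaction is silence, not a stated exclusion. Step 1 implies further steps, and the reference list includes work on interactions in nonlinear and count models. Neither shows that a term with baseline drinking was planned.

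A reader might also treat 30% as the baseline non-drinker share, or assume that a drinking majority swamps the effect. The 30% is an abstinence rate assumed for the power calculation, and the analysis plan says only that a large proportion did not drink. Headcount is not the weight either: in step 1, non-drinkers are 30% of students but carry 18.0/42.0 = 43% of the information. Dilution can be slight or substantial.

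Finally, stratifying does not isolate first use. A student with no recent drinking at baseline may have drunk before, and drinking outside the survey windows is missed. This objection stands and governs how the new estimate is labelled.

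**Conclusion.** The point holds as a gap between a stated hypothesis and the described analyses, and it should be addressed. Followed as written, the model cannot distinguish onset from a dry month at any non-drinker share strictly between 0 and 100%. That conclusion rests on the text alone.

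The sizes are illustrations under assumed rates. An onset odds ratio of 0.50 appears as about 0.57 to 0.87 (0.75 in the worked case), and a drinkers-only effect of the assumed size gives 0.63 with onset unchanged. The documents do not show which pattern applies. The pooled analysis is not invalid for any drinking; it does not answer the initiation question.

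**What to change.** 1. Define the initiation outcome as any past-30-day drinking at follow-up among students reporting none at baseline. State the baseline window, and say that this may include resumption as well as first use.
2. Add condition × baseline drinking status to the zero part of the peak-drinks model. Report the condition effect separately for baseline non-drinkers and drinkers, as an odds ratio and a risk difference with confidence intervals. Use the non-drinker estimate for the initiation hypothesis.
3. Keep the pooled effect as a summary of any drinking, and do not call it initiation.
4. Reconcile the two statements in Procedure on whether allocation used baseline drinking. The interaction is valid either way, since status was measured at baseline.

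**Cost.** No new data are needed. Three arms require two interaction coefficients, more if effects vary by follow-up, and the feedbacks-viewed strategy needs the same term if it is to speak to initiation. Precision is low: about 114 per arm if 30% are non-drinkers, which is an assumption. The stated .89 does not apply to this estimate, so the interval should carry the interpretation. The document describes completed work, so the analysis should be labelled post hoc if it is added after the data were seen.

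### The intent-to-treat comparisons of the amount drunk and the number of problems use only students with a non-zero value after randomisation, and no estimate of the amount over all students is planned

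*Combined protocol and SAP*

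**What the plan says.** The Statistical Analysis Plan describes hurdle models for peak drinks and problems. It says such models "independently predict zero versus non-zero counts in one part and values of non-zero counts in the other".

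- **Peak drinks.** In the first part, "the zero versus non-zero part of the model predicts whether individuals drank any alcohol using a logistic mixed model". For the amount, "The non-zero counts part of the model uses a truncated (i.e., zeros are removed, and values are subtracted by one) negative binomial mixed model".
- **Problems.** In the first part, "whether individuals experienced any alcohol-related problems or not was evaluated with a logistic mixed model". For the amount, "the number of problems among those who experienced any was examined with a truncated negative binomial mixed model".
- **Weekly drinks.** There is one part only: "Analyses examining the typical number of drinks consumed per week focused exclusively on counts, using a truncated negative binomial model". The stated reason is to avoid repeating the logistic part of the peak-drinks analysis.

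Under Modeling Treatment, the first strategy is labelled intent-to-treat, meaning that "outcomes were analyzed based on condition assignment, regardless of treatment participation and adherence". Outcomes are measured at the three follow-ups (Design). The Goals section expects less frequent alcohol feedback both to keep students from starting to drink and to lower consumption. The Power paragraph likewise plans for two effects: a 5-point difference in abstinence from an average of 30%, and a rate ratio of 1.2.

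**The concern.** Whether a student has a non-zero value at follow-up is itself an outcome. If feedback keeps some light drinkers at zero, or removes a student's only problem, those students leave the treated arm's count model while their counterparts stay in the control arm's. The treated mean among those who remain then rises with no harm to anyone. Analysing by assigned arm does not repair this, because membership of the comparison depends on what happened after assignment. Adjusting for baseline value, sex and site reduces the imbalance but cannot guarantee its removal.

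What is at stake is the conclusion about consumption. A benefit on abstinence can offset, or look like the reverse of, a benefit on amount. A reader who meets the count ratios under an intent-to-treat label will take them as effects in the randomised groups.

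**Working it through.** **Inputs from the documents.** Abstinence is 30%, so 70% drink; the abstinence difference is 5 points; the count effect is a rate ratio of 1.2 with power .87 (all from Power). Enrolment is 1,143 (Procedure), or 1,143/3 = 381 per arm if equal.

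**Assumed, because the documents give no values.** Drinkers' mean peak is 6. Students who switch to abstaining would have averaged 1 to 6 drinks. Half of students have a problem, with mean 4. Tests are two-sided at 5%. The 5 points are taken in the hypothesised direction, more abstinence under treatment; the Power paragraph words the difference as lower than control.

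**The plan's own figures.** The .87 cannot be reproduced, since no mean or dispersion is stated. Taken as given, it implies a standard error of ln(1.2)/(1.960 + 1.126) = 0.1823/3.086 = 0.0591, used below only as a scale. The .89 for abstinence was not reproduced: 400 per arm, 30% against 25%, gives .35, or .45 if n is divided by (1 − 0.25). Nothing below relies on it.

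**Who enters which comparison**

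| Outcome | All students | Non-zero at follow-up only | Amount over all students |
|---|---|---|---|
| Peak drinks | any drinking | amount | not stated |
| Problems | any problem | number | not stated |
| Weekly drinks | none | amount | not stated |

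**Peak drinks, every switcher a light drinker, nobody else changing.** The control all-student mean is 0.70 × 6 = 4.20. With switcher mean m, the treated all-student mean is 4.20 − 0.05m, and the mean among the remaining drinkers is (4.20 − 0.05m)/0.65.

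| m | Drinkers' mean | Drinkers-only ratio | All-student ratio |
|---|---|---|---|
| 1 | 4.15/0.65 = 6.38 | 1.064 | 0.988 |
| 2 | 4.10/0.65 = 6.31 | 1.051 | 0.976 |
| 3 | 4.05/0.65 = 6.23 | 1.038 | 0.964 |
| 4 | 4.00/0.65 = 6.15 | 1.026 | 0.952 |
| 6 | 3.90/0.65 = 6.00 | 1.000 | 0.929 |

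On the scale with one subtracted, the ratio for m = 2 is (6.31 − 1)/(6 − 1) = 1.062. If abstinence instead fell by 5 points, the bias would reverse: for m = 2, (4.20 + 0.10)/0.75 = 5.73, ratio 0.956, while the all-student mean rises 2.4%.

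**Problems, 5 points losing their only problem.** (0.50 × 4 − 0.05 × 1)/0.45 = 4.33, a ratio of 1.083 among those with any problem. The all-student mean falls from 2.00 to 1.95, or 2.5%.

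**A less extreme case.** In a simulation of 600,000 students, drinking status was only correlated with amount (0.3 to 0.9) and baseline was adjusted for. With no true effect in drinkers, the drinkers-only ratio was 1.007 to 1.030.

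**Consequences for testing, at standard error 0.0591 and a true ratio of 1/1.2 = 0.833**

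- Bias +1%: 0.842; |ln| = 0.172; 0.172/0.0591 − 1.96 = 0.96; power about .83.
- Bias +3%: 0.858; |ln| = 0.153; 0.153/0.0591 − 1.96 = 0.63; power about .73.
- Light-drinker case, m = 2: 0.833 × 1.051 = 0.876; |ln| = 0.132; 0.132/0.0591 − 1.96 = 0.28; power about .61.

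With no effect in continuing drinkers, biases of 1.007 to 1.030 give two-sided rejection of 5.2% to 7.9%. An unadjusted simulation of the light-drinker case (381 per arm, one follow-up, switcher means 2 and 1) gave 11.5% and 15.6%, against 4.8% with no shift in abstinence.

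**Weekly drinks.** Survey Measures defines peak as the most drunk on any one occasion in 30 days, and weekly drinking as the sum over the days of a typical week. A student can report zero for a typical week yet have drunk once that month. That student leaves the weekly model and still counts as a drinker in the peak logistic part, so a fall to zero in weekly drinking can go uncounted.

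**The case against.** The strongest defence is that the two-part structure fits the aims. Starting to drink and amount drunk are separate hypotheses and are powered separately. Hurdle models are a sound choice for outcomes with many zeros. The text openly says the count parts concern drinkers or those with a problem, and the peak-drinks and problems models, taken whole, analyse students by assigned arm. All of that stands. It does not supply an effect on amount in the randomised groups, and it does not cover weekly drinks.

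Four stronger readings are tempting but are not supported:

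- **That nothing compares all students.** The logistic parts do, on any drinking and any problem. The gap concerns amounts.
- **That the plan contradicts itself where it says "Data from all enrolled participants were utilized in the analyses".** That sentence (Modeling Time) goes on to speak of missing data and attrition. It is not a claim about zeros.
- **That the plan rules out combining the two parts.** Calling them independent is a general description of hurdle models. The plan is silent on a combined mean, which could be derived for peak drinks and problems but is not described.
- **That a ratio of 1.05, or power of .61, is the expected damage.** Both need every switcher to be a light drinker and nobody else to change.

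Power does not settle which estimate should lead. In simulations at 381 per arm and one follow-up, under assumed distributions, the all-student mean had power .82 against .66 for the drinkers-only count when both effects were present, but .64 against .79 when only drinkers changed. The plan also describes its models as chosen after the outcome distributions were examined, so demoting them now would be a post hoc change of main estimate.

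**Conclusion.** The point holds for the number of drinks and the number of problems. The count contrasts condition on a status that arises after randomisation and that the trial expects to move, and no stated analysis gives the arm difference in amount over all students.

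The principle is firm from the text; the size is not. For a 5-point shift in abstinence, a bias of about +1% to +3% in the drinkers-only ratio is the more general case, +3% to +6% is the light-drinker case, and zero applies if switchers drink the average amount. These figures rest on the assumed means and correlations. Whatever the bias, the all-student mean falls (by 1.2% to 7.1% in the peak-drinks table) and the plan as written would not report it. The change should be made because it decides what the trial can say about overall consumption. It is not a reason to discard the two-part models.

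**What to change.** For each of peak drinks, weekly drinks and problems, add an all-student intent-to-treat estimate: the ratio and the difference of means by assigned arm, zeros included, with the same covariates and errors clustered on student. Report it beside the two-part results, labelled as added after the outcome distributions were examined.

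Either of two routes will do:

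- a log-link marginal model with weighting or multiple imputation for dropout, since an unweighted marginal model generally needs stronger missing-data assumptions than the planned mixed models; or
- standardised means from a hurdle model whose two parts are fitted jointly with correlated random effects. Weekly drinks would need its own zero part for this.

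Describe the count-part ratios as applying among those who drank, or who had a problem, and not as intent-to-treat effects on consumption. Base any statement that the intervention lowered consumption overall on the all-student estimate.

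The cost is a paragraph in the plan and one extra model per outcome, with no new data. The all-student mean is less sensitive if the effect occurs only among drinkers (the .64 against .79 above), which is why the two-part results are kept.
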